7.2. Confirmation of eligibility for treatment

Eligibility for trial treatment will be confirmed centrally at UCL CTC after two cycles of first or second line salvage chemotherapy (four cycles if receiving treatment with brentuximab vedotin).

Evaluations should be carried out at sites as detailed in section 9.1 (Assessment of eligibility for nivolumab treatment). The results of these investigations will be used alongside the outcome of the central review of the patient's post-salvage PET-CT scan to confirm eligibility for trial treatment.

Following post-salvage evaluations, post-salvage case report form must be fully completed and faxed to UCL CTC. If a site is unable to send faxes, forms may be emailed to [contact]. The post-salvage case report form will be used to confirm patient

eligibility for trial treatment, and must be sent even if the patient is not eligible to receive nivolumab. If further information is required, UCL CTC will contact the person requesting registration to discuss the patient and request updated forms to be sent.

Registration [contact] Registration [contact]

Registration email address: [contact]

UCL CTC Office hours: 09:00 to 17:00 Monday to Friday,

excluding Bank Holidays

Please note that registration forms received after 16:00 may not be processed until the next working day

Once eligibility for trial treatment has been confirmed:

- UCL CTC will e-mail the main contact and pharmacy at site confirming that the patient may proceed with trial treatment.
- Eligible patients must be provided with a patient contact card. Site contact details for 24 hour medical care must be added to this card and patients advised to carry this with them at all times while participating in the trial.
- A GP letter should be sent to the patient's GP confirming that the patient is eligible for trial treatment (delete on GP letter template as applicable).

Where patients are not eligible for trial treatment:

- A GP letter should be sent to the patient's GP confirming that the patient is not eligible for trial treatment and that trial treatment will be given (delete on GP letter template as applicable).
- The patient will enter follow up for the purposes of the trial. See section 9.6.1 for details.

7.3. Initial Trial Drug Supply

Refer to Summary of Drug Arrangements for details of initial supply of Nivolumab for the trial.

8. TRIAL TREATMENT

Investigational Medicinal Products (IMPs)

For the purpose of this protocol, the IMP is Nivolumab (Opdivo®).

Non Investigational Medicinal Products (NIMPs)

There are no drugs defined as NIMPs for this trial.

8.1. Investigational Medicinal Products

Nivolumab (Opdivo®) will be provided free of charge by Bristol-Myers Squibb.

Nivolumab (Opdivo®) is licensed, but within this trial will be used outside its licensed indication.

Refer to the Summary of Drug Arrangements for detailed guidance on supply and storage of Nivolumab.

8.2. Treatment Summary

Patients for whom eligibility for treatment is confirmed (see section 7.2 for details) will receive 4-8 x 14-day cycles of nivolumab. Nivolumab 240mg will be administered on day 1 of each 14 day cycle. Dose banding is not permitted.

Trial treatment should begin within 4 weeks following the PET-CT scan to confirm eligibility for trial treatment (PET0).

	1	2	3	4	5	6	7	8	9	10	11	12	13	14
Nivolumab 240mg IV	Х													

Patients will have a PET-CT scan after 4 cycles (PET4). This should be performed on cycle 4, day 11-13 to allow time for central review before the cycle 5 day 1 visit would be due. Please note that patients must not proceed to cycle 5 prior to receipt of the PET4 central review report.

- If PET-negative (Deauville 1-3), they will stop nivolumab. Further management will be at the discretion of the treating clinician and the patient will be followed up as per the trial protocol (see section 9.6.2).
- If the scan shows disease progression, they will stop nivolumab and have further salvage at their treating clinician's discretion. They will enter into annual follow up for the trial.
- If the scan is positive (Deauville 4-5) but there is no evidence of disease progression, the patient will have a further 4 cycles of nivolumab. Following this, they will be followed up as per the trial protocol (see section 9.6.2).

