6.3.3. Pregnancy testing

All female participants who are WOCBP must have a negative serum or urine pregnancy test (minimum sensitivity 25 IU/I or equivalent units of HCG) at screening, following 2 cycles of salvage and and within 24 hours prior to starting nivolumab treatment. Pregnancy testing

^{*} HBsAb testing only required if standard of care locally.

should be repeated every 4 weeks during treatment, then at 1, 2 and 3 months post treatment. Pregnancy test results must be filed in the patient source data.

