 - Grade 4 drug-related endocrinopathy AEs which are adequately controlled with physiologic hormone replacement.
 - Electrolyte abnormalities that can be corrected and are not felt to be a cause for clinical safety concern.
- Progressive disease: for assessment of disease response see Appendix 3.

A treatment summary form must be completed and sent to UCL CTC promptly if treatment is discontinued. See section 9.5 for further details of investigations required when treatment is withdrawn. The patient will enter follow up as per the trial protocol (see section 9.6.2).

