9.6.2. Patients who receive nivolumab

Follow up in year 1 post treatment

Patients will be seen approximately once a month for the first 3 months, and every 3 months thereafter.

The following tests will be performed **1 month**, **2 months and 3 months** post treatment (30, 60 & 90 days after the last dose of Nivolumab respectively (±3 days)):

- Clinical examination
- Full blood count with differential
- Biochemistry (ALT/AST, total bilirubin, alkaline phosphatase, urea, creatinine, calcium, magnesium, sodium, potassium, LDH, albumin, urate, glucose)

- Tests for autoimmune conditions (amylase, lipase, ACTH)
- Thyroid function tests (TSH & Free T4; Free T3 to be performed if TSH/Free T4 abnormal)
- Adverse event assessment
- Pregnancy test (urine or serum; WOCBP only)
- Remission status assessment (investigations as per local policy) 3 month timepoint only

Blood samples for translational research

Blood samples are to be taken and sent to the central laboratory at the Weatherall Institute
of Molecular Medicine, Oxford at the 1 month post-treatment visit (30 days post last dose
of nivolumab (±3 days); see section 10.2 and Laboratory Manual for more details)

The following tests will be performed at months 6, 9 and 12 post treatment:

- Clinical examination
- Full blood count with differential
- Biochemistry (U&E, LFTs)
- Remission status assessment (investigations as per local policy)
- Assessment for late toxicity of nivolumab

In addition, at month 12 post treatment, the following test will be carried out:

Lung function test

Follow up from year 2 post treatment onwards

Patients will be seen annually. The following investigations will be performed:

- Remission status assessment (investigations as per local protocols)
- Assessment for late toxicity of nivolumab

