9.8. Follow up Assessments after Disease Progression

Following disease progression, patients will be seen annually. The following investigations will be performed:

- Remission status assessment (investigations as per local protocols)
- Assessment for late toxicity of nivolumab

N.B. confirmed disease progressions must be reported as urgent events within 72 hours of becoming aware (see section 12.5 (Urgent Events))

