12.2.1. Reporting of Adverse Events (AEs)

All adverse events that occur between the start of nivolumab treatment and 3 months post last nivolumab administration or commencement of next treatment for lymphoma (whichever is earlier) must be recorded in the the trial CRFs.

The reporting period has been selected as the patients are followed up at 1, 2, 3 months, then moving to 3 monthly follow up schedule. It is anticipated that most patients will have proceeded to further lymphoma treatment by the 3 month timepoint.

Adverse events meeting the definition of a Serious Adverse Event (SAE) or Adverse Event of Special Interest (AESI) must also be reported to UCL CTC using the trial specific SAE Report. Also refer to section 12.2.2 (Reporting of Serious Adverse Events (SAEs)) and section 12.4 (Adverse Events of Special Interest). Adverse events meeting the definition of an Urgent Event must also be reported on an Urgent Event form (also refer to section 12.5 Urgent Events).

Pre-existing conditions do not qualify as adverse events unless they worsen.

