12.4.1. Autoimmune events due to Nivolumab

The following adverse events of special interest for Nivolumab must be reported on the appropriate AE of Special Interest form within **24 hours of confirmed diagnosis.**

The following adverse events of special interest for Nivolumab must be reported on an SAE report form within **24 hours of confirmed diagnosis.** Please note that any signs and symptoms should be treated on their merits and reported as AEs/SAEs as applicable pending confirmation of diagnosis.

To summarise, the reporting requirements for **autoimmune events** based the treatment arm are as follows: (please note that the reporting window for autoimmune events differs to those for non-autoimmune SAEs; see section 12.2.2 for details).

Next Treatment	Reporting window for autoimmune toxicity
No treatment or further chemotherapy	From first administration of nivoumab until 5 months post last dose of trial treatment (or after this date if the investigator feels the event is related to nivolumab).
Autologous stem cell transplant	From first administration of nivoumab until 5 months post last dose of trial treatment (or after this date if the investigator feels the event is related to nivolumab).
Allogeneic stem cell transplant	From first administration of nivoumab until 5 months post last dose of trial treatment (or after this date if the investigator feels the event is related to nivolumab).
	Please note that colitis, dermatitis and hepatitis occurring after transplant day 0 should be reported as graft-versus-host disease in the first instance unless otherwise proven to be of autoimmune origin (see section 12.5 (Urgent Events) for details of reporting graft-versus-host disease).

Please note that confirmed autoimmune events must be reported to the CTC on an SAE report form even if the patient has received further treatment for their lymphoma within the 5 months after completing nivolumab.

Events will be collected as follows:

Event	Description See section 8.5 for detailed definitions	Form required	Timeframe
Autoimmune diarrhoea / colitis	Grade ≥2 diarrhoea persisting >48 hours and not suspected clinically or confirmed on lab testing to be due to infective causes	SAE report	Within 24 hours of confirmed diagnosis
Autoimmune uveitis	New or worsening inflammation of the eye, with ocular pain, erythema or blurring of vision.	SAE report	Within 24 hours of confirmed diagnosis

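### The protocol gives conflicting follow-up for nivolumab-treated patients who progress, so scheduled autoimmune and pregnancy testing may lapse while the reporting windows are still open

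*Protocol*

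**What the plan says.** Two sets of passages govern the same patient.

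**Annual follow-up.** Section 8.2 describes three outcomes of the scan after cycle 4. Patients with a negative scan, and patients who stay positive without progression and receive four more cycles, are followed under section 9.6.2. For patients with progression it says instead: "They will enter into annual follow up for the trial". Section 9.8 agrees: "Following disease progression, patients will be seen annually". It lists two items only, remission status and late toxicity of nivolumab.

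**Early visits kept.** Section 9.6.2, headed for patients who receive nivolumab, says: "Patients will be seen approximately once a month for the first 3 months, and every 3 months thereafter". Its visits at days 30, 60 and 90 carry clinical examination, blood count, biochemistry, amylase, lipase, ACTH, thyroid function, adverse event assessment and a pregnancy test. Progression is not an exception there or in Appendix 2.1. Section 8.4 includes among its reasons for permanent discontinuation "Progressive disease: for assessment of disease response see Appendix 3", and closes that list with "The patient will enter follow up as per the trial protocol (see section 9.6.2". Section 6.3.3 requires pregnancy tests during treatment, "then at 1, 2 and 3 months post treatment", for all women of childbearing potential.

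**Reporting windows.** Section 12.2.1 explains the 3-month adverse event window by the visits: "The reporting period has been selected as the patients are followed up at 1, 2, 3 months". Section 12.4.1 keeps autoimmune reporting open for 5 months after the last dose and adds that "confirmed autoimmune events must be reported to the CTC on an SAE report form even if the patient has received further treatment".

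**The concern.** Safety, with emphasis on autoimmune toxicity, is a named secondary endpoint (section 3.2), and section 18.2.2 plans to present autoimmune events of any grade. Section 12.4.1 defines several of these events by tests: raised transaminases or bilirubin, raised creatinine, and endocrine dysfunction with or without symptoms. Events of this kind may be found only if someone takes the blood sample.

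If a site acts on 8.2 and 9.8, a patient who progresses has no protocol-timed biochemistry, autoimmune, thyroid or pregnancy test after stopping nivolumab. A site acting on 8.4 and 9.6.2 does all of them three times. Ascertainment would then depend on which section the site read, and would be poorer in patients whose treatment failed.

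**Working it through.** The plan states no figure on this point, so there is none to reproduce. The check compares the passages and counts scheduled follow-up visits inside each window.

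**Inputs**
- Day 0 is the last nivolumab dose. One month is 365.25 / 12 = 30.44 days.
- Visits under 9.6.2: days 30, 60 and 90, then months 6, 9 and 12.
- Visits under 8.2 and 9.8: annual. The protocol does not say from which date the year runs for these patients. The first visit is assumed to fall about 12 months after the last dose (day 365).
- Adverse event window (12.2.1): 3 months = day 91, or the start of the next lymphoma treatment if earlier.
- Autoimmune window (12.4.1): 5 months = day 152, not shortened by further lymphoma treatment.
- Pregnancy reporting window for female patients (12.8): 6 months = day 183.

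**Count of scheduled follow-up visits on or before the end of each window**

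| Window | Under 9.6.2 | Under 8.2 and 9.8 |
|---|---|---|
| Adverse events, 3 months | 3 | 0 |
| Autoimmune, 5 months | 3 | 0 |
| Pregnancy, 6 months | 4 (3 with a pregnancy test) | 0 |

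The fourth visit in the last row is the month-6 visit, which falls at the end of that window and carries no pregnancy test.

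**How firm each row is**
- *Autoimmune:* firm. The window stays open whatever treatment follows, and section 12.2.2 says the separate rule exists so that immune-related events continue to be captured after a new lymphoma treatment starts.
- *Pregnancy:* firm as a contradiction. Section 6.3.3 requires three tests that section 9.8 does not schedule.
- *Ordinary adverse events:* weaker. Section 8.2 expects these patients to have further salvage. A patient who starts it before day 30 has left the window before the first visit, whichever section applies. The row matters for patients who start later or not at all.

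**Number of patients.** The protocol gives no progression rate on nivolumab. Assuming 10 to 30% of the 30 treated patients: 30 × 0.10 = 3 and 30 × 0.30 = 9.

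**Upper limit on the effect.** Let *p* be the true rate of autoimmune events that arise after treatment and are found only by testing, equal in all patients, and *f* the fraction who progress and are not tested. If none is detected in that fraction, the pooled rate observed is *p*(1 − *f*). The relative shortfall is *f*, so 10 to 30% under the assumption above. It is smaller if some progressors are tested locally or some sites follow 8.4. Events found at the on-treatment tests are not affected.

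**The case against.** The strongest reply is that the early visits are not removed. Sections 8.4, 9.6.2 and 6.3.3 and Appendix 2.1 all retain them, and a site could read the annual schedule as concerning disease status only. This stands to the extent that the defect is a contradiction. A reader of 8.2 alone might infer that the protocol deliberately drops safety visits for progressors, and the document as a whole does not support that. It does not settle the matter, because section 9.8 lists what is done after progression and safety blood tests are not on the list.

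Three further inferences go too far.
- *That these patients have no scheduled test and only spontaneous reporting.* Section 9.5 schedules a lung function test for progression after four cycles. Section 12.4.1 makes reporting of confirmed autoimmune events mandatory within 24 hours of diagnosis. Section 12.2 keeps the trial site responsible after transfer to a non-trial hospital. Section 9.8 keeps late-toxicity assessment. Patients on further salvage will also be seen locally. What is at risk is protocol-timed testing.
- *That toxicity could not be compared by response.* Section 18.2.2 plans no such comparison, and its safety analysis is descriptive.
- *That a visit at 5 months is missing.* No patient has one: section 9.6.2 goes from month 3 to month 6.

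**Conclusion.** The contradiction is real: 8.2 and 9.8 cannot be followed together with 8.4, 9.6.2, 6.3.3 and Appendix 2.1 for a nivolumab-treated patient who progresses. The consequence is clearest for autoimmune and pregnancy testing, with 0 scheduled follow-up visits against 3 in the 5-month autoimmune window, and 0 scheduled pregnancy tests against 3. It is weaker for ordinary adverse events.

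The likely direction is under-ascertainment, in progressors, of autoimmune events that are asymptomatic or defined by laboratory values, which lowers the pooled descriptive rate. The size cannot be fixed from the document. It rests on the assumed 10 to 30% progression (3 to 9 of 30 patients), on a first annual visit about 12 months after the last dose, and on sites following 8.2 and 9.8. The primary response rate, read from the scans after cycles 4 and 8, and the sample size are untouched. The wording should be corrected because a named safety endpoint depends on it.

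**What to change.** Reconcile sections 8.2 and 9.8 with sections 8.4, 9.6.2 and 6.3.3 and Appendix 2.1. In 8.2 and 9.8, state that annual follow-up after progression governs disease-status assessment only. State also that the existing safety assessments of 9.6.2 at 1, 2 and 3 months after the last dose are collected for every patient who received nivolumab, including those who stop for progression. Add a matching note to Appendix 2.1. The reporting windows in section 12 need no change.

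The cost is a wording amendment and up to three visits per progressing patient that are already in the schedule. On the assumption above that is at most 3 × 3 = 9 to 9 × 3 = 27 visits in total. Some of these patients will be on further treatment, so sites may need to fit the assessments around it.

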8.3. Trial Treatment Details

The IMP for this trial is nivolumab.

Patients who are PET positive following first or second line salvage will initially receive 4-8 cycles of single agent nivolumab.

Nivolumab will be given at a dose of 240mg as an intravenous infusion over 30 minutes on day 1 of each 14 day cycle.

There are no premedications recommended during the first cycle of nivolumab. If an acute infusion reaction occurs, subjects should be managed according to section 8.5 for subsequent cycles.

Every effort should be made to deliver treatment on time, however in exceptional circumstances (e.g. to allow for public holidays), it is permissible to bring treatment forward by up to 2 calendar days or to delay treatment for up to 3 calendar days. There should be no less than 12 days between doses. Treatment may be delayed for up to 4 weeks to allow for resolution of adverse events (see section 8.5 below).

8.4. Dose Modifications

Dose reductions and escalations of nivolumab are **not** permitted. Nivolumab should be delayed for up to 4 weeks for the following:

- Any ≥ grade 3 Haematological toxicity (Hb <80g/dl, platelets <50 x10⁹/l, neutrophils <1.0 x10⁹/l)
- Any ≥ grade 3 drug-related, non–haematological AE **except**:
 - o Fatigue
 - o Alopecia
 - Drug related endocrinopathies adequately controlled with physiologic hormone replacement.
 - Electrolyte disturbances that can be corrected and are unlikely to cause clinical safety concerns.
- Any grade 2 auto-immune complication including pneumonitis, renal dysfunction, diarrhoea/ colitis, neurological complication, derangement of liver function tests. Guidelines for management of auto-immune complications are set out in Section 8.5.
- Any non-drug related AE where the in the local investigator's opinion delaying treatment is in the patient's best interest.

Treatment may be resumed once AEs resolve to grade ≤1 or baseline value. If the criterion to resume treatment is met (see section 8.5), the subject should restart treatment at the next scheduled time-point, as set out in the protocol. If treatment is delayed by >4 weeks, the subject should be permanently discontinued from study therapy. Treatment may be discontinued earlier at the discretion of the investigator if it is felt that continuing on the trial treatment will compromise a successful outcome for the patient.

A treatment summary form must be completed and sent to UCL CTC promptly if treatment is discontinued. The patient will enter follow up as per the trial protocol (see section 9.6.2).

Treatment Discontinuation Criteria

Nivolumab treatment should be permanently discontinued for the following:

 ≥grade 2 drug-related uveitis or eye pain or blurred vision that does not respond to topical therapy. Uveitis is inflammation of the eye, and includes anterior uveitis (synonymous with iritis), posterior uveitis (comprising vitritis, choriditis, retinitis, chroioretinitis) and pan-uveitis (inflammation of the anterior chamber, vitreous, retina and choroid).

- ≥grade 3 pneumonitis
- Any grade 4 drug related AE or laboratory abnormality apart from the following:
 - Grade 4 neutropenia <7 days (G-CSF may be instituted, and continued until neutrophils exceed 1.5x10⁹/L, as per institutional policy)
 - Grade 4 amylase or lipase abnormalities that are not associated with clinical symptoms
 - Grade 4 drug-related endocrinopathy AEs which are adequately controlled with physiologic hormone replacement.
 - Electrolyte abnormalities that can be corrected and are not felt to be a cause for clinical safety concern.
- Progressive disease: for assessment of disease response see Appendix 3.

A treatment summary form must be completed and sent to UCL CTC promptly if treatment is discontinued. See section 9.5 for further details of investigations required when treatment is withdrawn. The patient will enter follow up as per the trial protocol (see section 9.6.2).

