8.5. Management of Adverse Events

8.5.1. Autoimmune complications

Because of its mechanism of action, autoimmune complications are common with nivolumab. Where sites have local policies for management of autoimmune toxicity, these may be followed. Where there is no local policy, suggested guidelines for management of such autoimmune complications are set out below. Clinicians are also advised to refer to the manufacturer's guidelines (see summary of product characteristics).

Autoimmune toxicities are regarded as AEs of special interest for this trial, requiring expedited reporting to UCL CTC. Please refer to section 12.4 for details of how and when to report autoimmune events.

If treatment is delayed by >4 weeks due to autoimmune toxicity, the subject should be permanently discontinued from study treatment.

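### Sections 8.4 and 8.5 of the protocol give inconsistent stopping rules for four grade 3 immune events, and contradict each other on severe endocrinopathy controlled on hormone replacement

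*Protocol*

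**What the plan says.** **Section 8.4, delay.** "Nivolumab should be delayed for up to 4 weeks for the following": among the triggers is "Any ≥ grade 3 drug-related, non–haematological AE". There are four exceptions: fatigue, alopecia, correctable electrolyte disturbance, and "Drug related endocrinopathies adequately controlled with physiologic hormone replacement". On restart, "Treatment may be resumed once AEs resolve to grade ≤1 or baseline value", and then: "If the criterion to resume treatment is met (see section 8.5), the subject should restart treatment at the next scheduled time-point".

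**Section 8.4, permanent stop.** A separate list of discontinuation criteria covers uveitis from grade 2 that does not respond to topical treatment, "≥grade 3 pneumonitis", most grade 4 drug-related events, and progression. The exceptions to the grade 4 rule include "Grade 4 drug-related endocrinopathy AEs which are adequately controlled with physiologic hormone replacement".

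**Section 8.5.1.** Local policies on autoimmune toxicity may be followed. "Where there is no local policy, suggested guidelines for management of such autoimmune complications are set out below". Each table has one column for the action on trial treatment and another for recommended management of the toxicity.

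**Section 8.5.3.** pDILI is a permanent stop.

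**The concern.** Two adjacent sections tell an investigator what to do with nivolumab after an immune event, and for several events they differ. Section 8.4 is headed as the dose-modification section, is written as a directive and has its own stop list. That list names grade 3 pneumonitis and otherwise sets the general threshold at grade 4, so a reader would take other grade 3 immune events to be holds from which treatment can restart. The tables in 8.5.1 are stricter, but their introduction calls them suggestions.

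At stake is whether a patient is rechallenged after a serious immune toxicity. For controlled severe endocrinopathy, it is whether dosing continues at all. With 30 planned sites (section 1.1), practice could differ from site to site. Section 14.1 has central monitoring escalate cases in which dose-modification rules were not followed, and that check needs a single rule to check against.

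**Working it through.** No arithmetic applies. The check compares the two sections event by event. In the 8.4 column, delay means a hold of up to 4 weeks with restart permitted.

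| Event | 8.4 | 8.5 | Result |
|---|---|---|---|
| Grade 3 diarrhoea/colitis | Delay | Permanent stop (8.5.1.1) | Differ |
| Grade 3 pneumonitis | Permanent stop | Permanent stop (8.5.1.2) | Agree |
| Grade 3 hepatitis | Delay | Permanent stop (8.5.1.3) | Differ |
| Grade 3 rash | Delay | Delay (8.5.1.4) | Agree |
| Grade 3 renal | Delay | Delay (8.5.1.6) | Agree |
| Grade 3 neurological | Delay | Permanent stop (8.5.1.7) | Differ |
| Grade 3 myocarditis | Delay | Permanent stop (8.5.1.8) | Differ |
| First grade 3 other immune reaction | Delay | Delay (8.5.1.8) | Agree |
| Recurrent grade 3 other immune reaction | No rule on recurrence | Permanent stop (8.5.1.8) | Omitted from 8.4 |
| pDILI | Not listed | Permanent stop (8.5.3) | Omitted from 8.4 |
| Grade 3 adrenal insufficiency, controlled on replacement | No delay, no stop | Permanent stop (8.5.1.5) | Contradict |
| Grade 4 adrenal insufficiency, hypothyroidism, hypophysitis or diabetes, controlled on replacement | No delay, no stop | Permanent stop (8.5.1.5) | Contradict |
| Grade 3 hypothyroidism, hypophysitis or diabetes, controlled and without symptoms | No delay | Continue on replacement (8.5.1.5) | Broadly agree |

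**Non-endocrine events.** There are nine grade 3 rows. Four agree, four differ, and one (recurrence) is an omission. The ungraded row for severe skin syndromes in 8.5.1.4, and the lines on persistent grade 2-3 events and steroid dependence in 8.5.1.8, were not counted.

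**Endocrine events.** The sentence in 8.5.1.5 on continuing alongside hormone replacement sits in the row for symptomatic, lower-grade disease. The severe row has no such sentence. An express exemption in 8.4 therefore meets an unconditional stop in 8.5.1.5. At grade 3 the conflict is confined to adrenal insufficiency.

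**pDILI.** It begins at AST or ALT above 3 x ULN with bilirubin above 2 x ULN. Those values overlap the grade 2 hepatitis row of 8.5.1.3 (AST/ALT 3-5 x ULN and/or bilirubin 1.5-3 x ULN), where treatment is delayed and may restart. Someone working only from the 8.4 lists would not see that pDILI is a stop.

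**The case against.** The strongest reply is that 8.4 states a general rule and 8.5 a specific one. The delay bullet covers everything from grade 3 upwards, including grade 4 events and grade 3 pneumonitis, which 8.4 itself stops a few lines later. Being in that bullet cannot by itself mean that restart is allowed. Restart is permissive, and both 8.3 and 8.4 point to 8.5. For the four grade 3 events, 8.5 offers no restart criterion, only a stop. On this reading 8.4 holds the drug and 8.5 never releases it.

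Much of this stands. It makes it likely that 8.5 is meant to govern the four events. It does not settle the matter: no sentence gives 8.5 precedence, 8.4 keeps a separate stop list that omits them, and 8.5.1 introduces its tables as suggestions. Local policy is mentioned only in the management column of the tables, so the action column may well be meant as binding, but the introduction does not say so. The argument also fails for the endocrine case. Where 8.4 requires no delay, there is no restart criterion to look up.

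There are safeguards. Autoimmune events go to the trials unit on an SAE report within 24 hours of confirmed diagnosis (12.4.1), usually well inside a 14-day cycle, and the trial management group reviews full SAE listings (18.2.2). These make an unnoticed rechallenge less likely, but they do not tell the unit which rule applies.

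A reader might infer that every recurrent grade 3 immune event is in conflict. The documents do not support that: the recurrence rule belongs only to the table of other reactions in 8.5.1.8, and 8.4 is silent on recurrence rather than opposed to stopping.

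**Conclusion.** The inconsistency is real and should be corrected. It comes to four grade 3 events that 8.5.1 stops and the 8.4 stop list leaves out, one direct contradiction on severe endocrinopathy controlled on replacement, and two omissions (pDILI, and recurrent grade 3 reactions under 8.5.1.8).

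A reader might infer that the protocol mandates unsafe dosing. It does not: restart under 8.4 is optional, and a site that follows the stricter 8.5 table satisfies both sections. The risk is uneven rechallenge between sites and, in the other direction, loss of bridging treatment for a patient whose controlled endocrinopathy 8.4 would let continue.

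A reader might also infer an effect on the overall response rate. None can be shown. The protocol does not say how often these events are expected; section 2.1 gives only an overall grade 3 rate of 16-22% from earlier studies, not split by event.

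The conclusion rests on the wording alone and assumes that no other trial document states which section prevails.

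**What to change.** 1. Add grade 3 diarrhoea/colitis, hepatitis, neurological toxicity and myocarditis, and pDILI, to the permanent-stop list in 8.4. Add recurrent grade 3 events only for the other reactions covered by 8.5.1.8; a wider entry would newly stop recurrent grade 3 rash or renal events.
2. State that for non-endocrine immune events the trial-treatment action column in 8.5 prevails over the general rule in 8.4, and that local policy may replace only the toxicity-management column.
3. Have the clinical team choose one rule for severe endocrinopathy controlled on hormone replacement and write it identically in 8.4 and 8.5.1.5. The precedence sentence should leave endocrine events out, because it would otherwise settle this clinical question by default.

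The cost is a few lines at the next amendment, a short clinical decision and a notice to sites. No new data or assessments are needed.
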